Appendix D: Pre-Operative Assessments

Subject ID:	Date:	Time:	Interviewer:
-------------	-------	-------	--------------

- 1) How much pain you are experiencing at this time. (make an X on the line)

very little _____ very much

2) How satisfied are you with your pain relief at this time?	Very unsatisfied 1	Somewhat unsatisfied 2	Neutral 3	Somewhat satisfied 4	Very Satisfied 5
3) How much nausea are you experiencing at this time?	No nausea 1	Very little 2	Mild 3	Moderate 4	Severe nausea 5
4) How much vomiting are you experiencing at this time?	No vomiting 1	Very little 2	Mild 3	Moderate 4	Severe vomiting 5

- 5) Have you experienced any other symptoms, besides pain, since you were given the study medications?
- NO
 - YES. If yes, please describe: _____

State Trait Anxiety Inventory (STAI) – State Items

Read each statement and select the appropriate response to indicate how you feel right now, that is, at this very moment. There are no right or wrong answers. Do not spend too much time on any one statement but give the answer which seems to describe your present feelings best.

		Not at all	A little	Somewhat	Very much so
1	I feel calm	1	2	3	4
2	I feel secure	1	2	3	4
3	I feel tense	1	2	3	4
4	I feel strained	1	2	3	4
5	I feel at ease	1	2	3	4
6	I feel upset	1	2	3	4
7	I am presently worrying over possible misfortunes	1	2	3	4
8	I feel satisfied	1	2	3	4
9	I feel frightened	1	2	3	4
10	I feel uncomfortable	1	2	3	4
11	I feel self confident	1	2	3	4
12	I feel nervous	1	2	3	4
13	I feel jittery	1	2	3	4
14	I feel indecisive	1	2	3	4
15	I am relaxed	1	2	3	4
16	I feel content	1	2	3	4
17	I am worried	1	2	3	4
18	I feel confused	1	2	3	4
19	I feel steady	1	2	3	4
20	I feel pleasant	1	2	3	4

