1.1.2 Objectives and hypotheses

Objective 1: To compare the effect of gabapentin 600 mg to placebo on intraoperative pain during D&E under moderate sedation.

We hypothesize that administration of gabapentin will lower reported pain during D&E compared to placebo.

Objective 2. To compare the effect of gabapentin 600 mg to placebo on the total dose of IV sedation (fentanyl and midazolam) during D&E.

We hypothesize that administration of gabapentin will reduce the total dose of IV sedation agents compared to placebo.

Objective 3. To compare the effect of gabapentin 600 mg to placebo on pre- and post-operative pain, anxiety, nausea, vomiting, and overall satisfaction with pain management.

We hypothesize that administration of gabapentin will result in lower pre- and post-operative pain, anxiety, nausea, and vomiting, and higher satisfaction with pain management compared to placebo.

Objective 4. To compare the adverse events and risks of gabapentin to placebo.

We hypothesize that pre-operative administration of gabapentin will not increase adverse events compared to placebo.

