alprazolam 0.25 mg, promethazine 25 mg, and azithromycin 500 mg. Medications may be adjusted per provider judgement and patient characteristics, such as allergies. At the time of D&E, providers will administer a paracervical block using 20 mL of 1% lidocaine with 4 units vasopressin. Initial doses of moderate sedation at both sites will be 1 mg midazolam and 50 mcg fentanyl. Additional doses are sometimes required intraoperatively to achieve adequate pain relief and will be left to provider discretion. Total doses of moderate sedation will be capped at 5 mg midazolam and 200 mcg fentanyl. Total doses of midazolam and fentanyl will be documented.

Assessments and tools:

Pain will be assessed using 100-mm VAS. We will assess pre-operative pain using VAS while the patient awaits moderate sedation administration in the procedure room. We will assess intra-operative pain at the following time points: within one minute after speculum placement, within one minute after the initiation of uterine suction aspiration, and within one minute after speculum removal. An assessment of “maximum” intra-operative pain will be made 3- 5 minutes after speculum removal. VAS will be used to assess post-operative pain 30 minutes (range 20-40 minutes) after the procedure. Assessments of anxiety will be made using 20-items of state anxiety from the State Trait Anxiety Inventory (STAI), a validated tool for measurement of anxiety that is used frequently in abortion research [19], [20]. Anxiety will be assessed prior to administration of moderate sedation and 30 minutes post-procedure. Nausea, vomiting, and satisfaction with pain control will be assessed using 5-point Likert scale prior to the administration of moderate sedation and 30 minutes post-procedure. Lowest intra-operative oxygen saturation as measured via pulse oximeter and administration of reversal agents will be recorded. Adverse events will be monitored and include, but are not limited to, seizure-like activity, need for sedation reversal agent, respiratory depression (oxygen saturation <90%), use of uterotonics, aspiration of emesis, or transfer to hospital. Overall satisfaction with pain control will also be assessed on POD1 using a 5-point Likert scale. Participants will receive financial compensation in the form of a \$40 gift card on the day of the procedure for their time and participation. After completion of the phone assessment on POD1, participants will be mailed a \$10 gift card.

Table 1: Assessments

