Time	VAS	STAI	Nausea, vomiting, and satisfaction 5-point Likert
Pre: Prior to moderate sedation	X	X	X

Intra-op: Within 1 minute after speculum insertion	X		
Intra-op: Within one minute after initiating uterine aspiration	X		
Intra-op: Within 1 minute after speculum removal	X		
Max pain experienced during abortion procedure, assessed 3-5 min after speculum removal (Primary outcome)	X		
Post: 30 min after D&E completion	X	X	X
POD1			X (satisfaction only)

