1.3.5 Admission procedure

After eligibility has been confirmed and informed consent has been obtained, participants will complete a questionnaire assessing demographic information and medical history (Appendix C). Relevant baseline characteristics including age, gravidity, parity, race, ethnicity, and weeks of gestation will be collected. We will also document pre-existing psychiatric disorders such as depression, anxiety, bipolar disorder and chronic pain syndromes.

She will then be assigned to the next sequentially numbered randomization packet. After initiation of cervical preparation, the participant will consume the study drug from the packet with water or clear juice. Time of administration will be recorded on the patient's chart and will occur at least one hour before the planned procedure. All medications given throughout the clinic experience will be recorded. Method(s) of cervical preparation will be recorded. Antibiotic, anti-emetic, and analgesic administration will be standardized but medications may be adjusted to the need of each woman to accommodate patient characteristics such as allergies and without regard to her enrollment in this study.

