1.3.6 Follow-up procedure

The pre-operative assessment will be completed by the study coordinator immediately prior to initiation of moderate sedation (Appendix D), which usually occurs in the procedure room. The intra-operative assessments will be administered by the study coordinator during the procedure at the specified time or point during the procedure (Appendix E). The times of all assessments will be noted. The time of speculum removal will be considered the time of procedure completion.

A same-day post-operative assessment will be completed by the participant 30 minutes (20-40 min range) after procedure completion in the recovery room (Appendix F). After completion of the post-operative assessment patients will receive a \$40 gift card and be reminded that they will receive a phone call the following day.

A phone call will be made to all participants on the day following their procedure to administer the POD1 assessment (Appendix G). The participant phone number will be tested at the time of enrollment and three attempts will be made to reach participants by phone on POD1. Participants will be provided with a phone number for the study coordinator should they have trouble receiving phone calls. Patients that complete the POD1 assessment will be mailed a \$10 gift card.

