1.3.7 Criteria for discontinuation

Participants may withdraw at any time by refusing to participate in further assessments or by electing not to continue with pregnancy termination.

We expect loss to follow up for all primary and most secondary outcomes to be rare as most assessments are made on the date of study enrollment. We expect some loss to follow up for the POD1 assessment but will take the following steps to minimize this loss: testing of participant phone numbers at the time of enrollment, providing a reminder about the phone call prior to clinic discharge, agreeing in advance on a convenient time for the follow up phone call, providing participants with the study coordinators phone number, and provision of a gift card by mail after completion.

Patients who experience serious adverse events will be discontinued from the study and allocation may be revealed to ensure appropriate management of medical conditions. An adverse event (AE) is defined as any health-related reaction, effect, toxicity or abnormal laboratory result that a study participant experiences during the course of the study, irrespective of relationship to the study intervention. A serious adverse event (SAE) is defined as any experience that is fatal or life threatening, requires in-patient hospitalization or prolongation of an existing hospitalization, or results in a persistent or significant disability or incapacity.

A data safety monitoring board (DSMB) will be assembled. A DSMB meeting will be triggered by a case of respiratory compromise requiring sedation reversal (naloxone or flumazenil). This board will consist of clinicians and researchers knowledgeable in abortion care, moderate sedation, and gabapentin. The following individuals have agreed to serve on the DSMB:

- [name], Professor of Obstetrics and Gynecology, Division Director of Family Planning, University of California Davis

- [name], MPH, Senior Director of Medical Services, PPFA
- [name], PhD, Professor of Anesthesia/Dean, University of California San Francisco

If triggered to meet, they will review the cumulative data to date and provide advice regarding the safety of continuing, modifying, or discontinuing the study.

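### The only scored vomiting item for Objective 3 asks about the present moment, at two moments, so vomiting that has already stopped may be recorded as none

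*Combined protocol and SAP*

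**What the plan says.** Objective 3 (section 1.1.2) expects gabapentin to give "lower pre- and post-operative pain, anxiety, nausea, and vomiting, and higher satisfaction with pain management". Section 1.3.1 states that "Nausea, vomiting, and satisfaction with pain control will be assessed using 5-point Likert scale", before moderate sedation and 30 minutes after the procedure. Table 1 repeats this in the column "Nausea, vomiting, and satisfaction 5-point Likert", which on post-operative day 1 (POD1) covers satisfaction only.

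Item 4 has the same wording on the pre-operative form (Appendix D) and the post-operative form (Appendix F): "How much vomiting are you experiencing at this time". It is scored from 1 (none) to 5 (severe). The intraoperative form (Appendix E) has no vomiting item.

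On timing, section 1.3.5 says that taking the study drug "will occur at least one hour before the planned procedure". Section 1.3.6 says: "The pre-operative assessment will be completed by the study coordinator immediately prior to initiation of moderate sedation". Appendix F is completed 20 to 40 minutes after the procedure.

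Section 1.3.10 gives secondary outcomes chi-square and t-tests as applicable. It does not say what the vomiting variable is.

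**The concern.** Pain, nausea and anxiety are states that can be rated at a moment. Vomiting is an event. A question about the present moment, asked twice, shows who is vomiting at those two moments. It need not show who vomited after the drug, during the procedure or in early recovery.

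If most episodes are over when the question is put, few women in either arm will score above the lowest category. A null result would then say little about the hypothesis, and could be misread as showing little vomiting in both arms. Rebuilding the outcome later from free text, adverse event reports and the medication log would be partial and would follow no stated rule.

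**Working it through.** **1. Time that the two readings stand for.** At least 60 minutes from drug to planned procedure (section 1.3.5), plus at least 20 minutes from procedure to post-operative form (Appendix F): 60 + 20 = 80 minutes, plus the procedure itself.

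**2. Where vomiting that has stopped could still appear.**

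| Source | Looks back? | Names vomiting? | Feeds Objective 3? |
|---|---|---|---|
| Appendices D and F, item 4 | No | Yes | Yes |
| Appendices D and F, item 5 (symptoms other than pain since the drug) | Yes | No; free text | Not stated |
| Appendix G, item 9 (side effects, POD1) | Yes | No; free text, only women reached | Not stated |
| Adverse event reports (sections 1.3.1, 1.3.7) | Yes | No; the examples name aspiration of emesis | Not stated |
| Medication log (Appendix C) | Yes | No; records nausea medication given | Not stated |

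The one source that scores vomiting does not look back. The sources that look back neither ask about it by name nor enter the outcome.

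**3. The plan's own figure.** The documents give no vomiting rate or power. The only sample size is for pain (section 1.3.11): SD 25, difference 13, 80% power, alpha 0.05. Taken as two-sided, n per arm = 2 × (1.960 + 0.842)² × 25² / 13² ≈ 58.1, rounded up to 59, as stated. The vomiting point does not alter it. Enrolment of 130 at 1:1 gives 65 per arm.

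**4. Illustration of the loss.** Assumptions, none from the documents: placebo risk of any vomiting is 10, 20, 30 or 40%; gabapentin halves it; and the same fraction of vomiters is captured in both arms. Expected placebo count = 65 × risk × fraction captured. Power is by exact binomial enumeration, uncorrected Pearson chi-square, two-sided 0.05.

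| Placebo risk | Women who vomit (65 × risk) | Counted if 10–50% captured | Power, all captured | Power, 25% captured |
|---|---|---|---|---|
| 10% | 6.5 | 0.65–3.25 | 0.19 | 0.04 |
| 20% | 13 | 1.3–6.5 | 0.35 | 0.10 |
| 30% | 19.5 | 1.95–9.75 | 0.54 | 0.14 |
| 40% | 26 | 2.6–13 | 0.72 | 0.19 |

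**5. What full capture would buy.** Fisher's exact test with all episodes captured has power 0.10, 0.28, 0.46 and 0.64 at the four risks. The 95% half-width for the risk difference is 1.96 × √[(p₁(1−p₁) + p₂(1−p₂))/65]. At 20% v 10% this is 1.96 × √[(0.16 + 0.09)/65] = 0.122. Across the four risks it is about 9, 12, 14 and 15 percentage points.

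**The case against.** The strongest reply is that the loss is inferred from wording. The response options grade vomiting from slight to severe, which fits poorly with a single instant, so some women may answer for the current phase of care. The coordinator completes the pre-operative form and could clarify. This stands: the documents show that stopped vomiting may be scored as none, not that it will be. If women differ in how they read the item, though, the window varies between them and is unknown.

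Item 5 expressly excludes only pain and covers the whole time since the drug, so past vomiting is reportable there. The adverse event definition, "any health-related reaction, effect, toxicity or abnormal laboratory result that a study participant experiences during the course of the study", would also cover it. Both points stand, so a reader who infers that stopped vomiting goes wholly unrecorded goes too far. But item 5 asks for other symptoms directly after the nausea and vomiting items, which may discourage repeating them, and no rule carries the answer into the outcome. The adverse event examples, "use of uterotonics, aspiration of emesis, or transfer to hospital", do not name vomiting itself.

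Objective 3 names pre- and post-operative vomiting, not cumulative vomiting since the drug, and section 1.3.1 specifies two ratings. That also stands. The cumulative outcome proposed below suits an event better; it is not what the plan promised and then failed to deliver.

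A reader might also infer bias toward one arm. The documents do not support that: the same item is used, blinded, in both arms, and what can be expected is lost sensitivity.

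**Conclusion.** The point holds as a mismatch between an event outcome and a present-moment question. Under-counting in both arms is likely, but its size cannot be known from the documents. The fall in power, from 0.19–0.72 to about 0.04–0.19, rests on the assumed risks, a halving of risk and a capture fraction of one quarter.

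The reach is small: one part of one secondary objective. The primary outcome, sample size and safety monitoring are untouched. The nausea item shares the wording, but nausea can be rated at a moment, so the point does not extend to it. Low priority, worth making because it is cheap and because missed episodes cannot be reliably recovered once the forms are completed.

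**What to change.** Keep the five response options and change only the time window.

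- **Appendix D, item 4:** 'How much vomiting have you had since you took the study medication?'
- **Appendix F, item 4:** 'How much vomiting have you had since the questionnaire you answered just before your sedation?' Appendix E falls between the two forms, so 'since the last questionnaire' would be ambiguous.
- **Appendix E:** add 'Vomiting seen during the procedure: yes/no', completed by the coordinator, who is already in the room throughout (section 1.6).
- **Section 1.3.10:** 'The main vomiting comparison is the proportion with any vomiting from study medication to the post-operative form, defined as any answer above the lowest category on Appendix D or F, or vomiting seen on Appendix E, with a risk difference and 95% CI, by chi-square or by Fisher's exact test if counts are small. Vomiting before sedation (Appendix D) and from sedation to the post-operative form (Appendix E or F) will be reported as supporting results.'
- **Section 1.3.1 and Table 1:** matching edits.

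The cost is one reworded item on each of two forms, one tick-box and two sentences in the analysis section, with no added visit, questionnaire or participant.

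Downsides: women must recall across sedation. Recall could differ by arm if gabapentin adds sedation, which the protocol itself anticipates; the tick-box covers the procedure but not recovery. Vomiting after the post-operative form stays unscored, as now. Power stays low if vomiting is uncommon: at 65 per arm with risk halved from an assumed 10 to 20%, Fisher power is about 0.10 to 0.28.

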of rescue analgesic, and reduced intraoperative pain scores [18]. They did note increased dizziness in the gabapentin group. Gabapentin has also been found to improve pain scores and decrease consumption of fentanyl when used for pain control during intensive care unit admission [15]. Dose-finding studies have been limited by inadequate sample size, but their findings suggest that pre-operative doses of at least 600 mg to 900 mg provide post-operative benefit [5].

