1.3.4 Description of the drugs and devices to be studied

Gabapentin (Neurontin®) is FDA-approved for the treatment of post-herpetic neuralgia and seizure disorder. Off-label uses include chronic refractory cough, neuropathy, hot flashes, restless leg syndrome, social anxiety disorder, and post-operative pain. Although its chemical structure is similar to GABA and it was originally suspected to be a GABA analog, the primary mechanism of action is suspected to be via central nervous system voltage-gated calcium channels and the inhibition of excitatory neurotransmitter release [21]. In the U.S., it is available as 100 mg, 300 mg, and 400 mg capsules or 600 mg or 800 mg tablets and is intended for oral consumption. Although originally brought to market as Neurontin® by Pfizer, gabapentin is now available as a generic from multiple pharmaceutical companies. A single 600 mg tablet costs less than \$5 wholesale. Oral consumption leads to a peak serum concentration in 2-4 hours with a half-life of 5-8 hours [5].

Gabapentin has an impressive safety record. It is metabolized renally and should be dose-adjusted for renal impairment [5]. Drug interactions are uncommon but include decreased absorption when consumed with antacids [5]. The most commonly reported side effects include dizziness, somnolence, ataxia, and edema and are more pronounced with chronic use and dose ≥ 1200 mg [22]. Adverse events are uncommon and include seizure or worsening depression at the time of chronic gabapentin use cessation [5]. Recently, concerns regarding respiratory depression have been raised due

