Appendix G: Post-operative day 1 assessment

Subject ID:	Date:	Time:	Interviewer:
-------------	-------	-------	--------------

8) On a scale of 1 to 5, where 1 is very unsatisfied and 5 is very satisfied, how satisfied were you with the pain relief you experienced yesterday?

- 1 very unsatisfied
- 2
- 3
- 4
- 5 very satisfied

9) Did you experience any complications or side effects yesterday or today?

- NO
- YES

If yes, please explain: _____

10) Would you choose this method of pain control if you need to have this procedure again?

- NO
- YES

11) Would you recommend this method of pain control to other women who are having this procedure?

- NO
- YES

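### Dizziness and unsteadiness, known effects of gabapentin, can be recorded only as free text, which is likely to under-record them in both arms and lean Objective 4 towards finding no increase

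*Combined protocol and SAP*

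**What the plan says.** Section 1.1.2 sets the aim, "Objective 4. To compare the adverse events and risks of gabapentin to placebo", and the expectation: "We hypothesize that pre-operative administration of gabapentin will not increase adverse events compared to placebo".

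The background describes what the drug may do. Section 1.3.4: "The most commonly reported side effects include dizziness, somnolence, ataxia, and edema and are more pronounced with chronic use". The same sentence adds doses of 1200 mg or more to chronic use. Section 1.2, on the one cited study of gabapentin with sedation during a procedure: "They did note increased dizziness in the gabapentin group".

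The forms ask about such symptoms three times, each time as yes/no with space to describe:

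- Appendix D item 5, before moderate sedation: "Have you experienced any other symptoms, besides pain, since you were given the study medications".
- Appendix F item 5, 20-40 minutes after the procedure: the same wording.
- Appendix G item 9, by telephone on the day after: "Did you experience any complications or side effects yesterday or today".

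Nausea and vomiting each have a named item, graded 1 to 5, in Appendices D and F.

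**The concern.** Dizziness and unsteadiness are non-serious symptoms that staff may not see and that a participant may not think to mention when asked a general question. On the same pages, nausea and vomiting are asked about by name and graded. Symptoms where benefit is hoped for are therefore measured more closely than the symptoms the background gives most reason to expect as harms.

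At stake is how a null result under Objective 4 is read. Section 1.7 says the trial will add to knowledge of gabapentin's safety alongside moderate sedation in outpatients. If non-serious effects are under-recorded in both arms, the absolute difference is too small and the finding leans towards the hypothesis. Symptoms not asked about at the time cannot be reliably recovered later.

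**Working it through.** **1. Where each symptom can be recorded (Appendices C to G)**

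| Symptom | Before sedation (D) | 20-40 min after (F) | Next day (G) |
|---|---|---|---|
| Nausea | named, 1-5 | named, 1-5 | free text |
| Vomiting | named, 1-5 | named, 1-5 | free text |
| Dizziness | free text | free text | free text |
| Unsteadiness | free text | free text | free text |

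The STAI statement about feeling steady belongs to the anxiety score and does not measure ataxia.

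**2. The plan's own figure.** Section 1.3.11 gives a sample size for pain only. With a difference of 13, SD 25, 80% power and two-sided 5%:

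n per arm = 2 × (1.960 + 0.842)² × 25² / 13² = 58.05, rounded up to 59.

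This matches the plan (a one-sided test would need 46), so two-sided 5% is used below. The point does not affect this figure. The plan states no rate, margin or power for Objective 4.

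**3. Effect of partial recording.** Let p1 and p0 be the true proportions with dizziness on gabapentin and placebo, and s the share of true cases that gets recorded. The arms are blinded, so s is taken as equal in both.

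- Observed proportions: s·p1 and s·p0.
- Observed difference: s·(p1 − p0), smaller than the true difference whenever s is below 1.

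The direction therefore does not depend on the rates chosen. The size does.

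**4. Illustration.** The arm size is 130 / 2 = 65. The test is the uncorrected chi-square (pooled z), two-sided 5%, with power found by exact enumeration of the two binomials. All rates and all values of s are assumptions.

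| True rates | s = 1 | s = 0.75 | s = 0.5 |
|---|---|---|---|
| 30% vs 10% | 83% | 22.5% vs 7.5%: 68% | 15% vs 5%: 49% |
| 40% vs 20% | 72% | 30% vs 15%: 54% | 20% vs 10%: 35% |
| 20% vs 10% | 35% | 15% vs 7.5%: 27% | 10% vs 5%: 19% |

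In the first row the 20-point difference becomes 10 points at half capture. At one-third capture (10% vs 3.3%) power is 33%. In the last row power is low even with complete recording.

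**5. Adding background dizziness.** Suppose co-medication causes dizziness in an assumed 20% of women in both arms, independently of the study drug.

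- Placebo: 1 − 0.8 × 0.9 = 28%.
- Gabapentin: 1 − 0.8 × 0.7 = 44%.

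Full recording then gives 49% power. If the open question records half of the same symptoms (14% vs 22%), power is about 21%.

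**The case against.** The strongest reply has four parts.

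*The inquiry is not negligible.* Symptoms are asked about directly on three occasions, and the Appendix D question comes before any IV midazolam or fentanyl. A reader might infer that harms rest on one question, or on recall after sedation throughout. The documents support neither: only Appendix F is answered shortly after IV sedation.

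*The background is weaker than it first looks.* Section 1.3.4 ties the side effects more to chronic use and higher doses, while this trial gives a single 600 mg dose. Section 1.2 gives no rate for the dizziness it reports. This stands, and it is why no size can be claimed.

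*Prompting also collects background dizziness.* Participants generally receive alprazolam and promethazine as well as midazolam and fentanyl. The 28% vs 44% case has the same 49% power as the half-capture case without background. That comparison gives background dizziness to the prompted item only. The open question asks about any other symptom, so it too can pick up dizziness from co-medication. On equal terms the figures are 49% and about 21%. What stands is that the net gain depends on unknown rates.

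*Other harms are recorded.* Lowest oxygen saturation, reversal agents, uterotonics and discharge time have fields, and over-sedation is partly caught by the tick boxes beside each intra-operative VAS. Section 1.3.1 also lists seizure-like activity, aspiration of emesis and transfer to hospital, and these have no field in Appendices C to G. A reader might infer that they would be lost. The documents do not support that: section 1.3.1 says such events will be monitored, the coordinator stays in the room for the procedure (section 1.6), and a co-investigator reviews all adverse events (section 1.3.7). Staff would witness them.

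**Conclusion.** The point holds for non-serious effects such as dizziness and unsteadiness. They are named in the background, have no item of their own, and reach the data only as free text. Under-recording is likely rather than certain. If it is equal in the two blinded arms, it shrinks the absolute difference and favours the no-increase hypothesis.

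The size is unknown. The drop from 83% to 49% power rests wholly on assumed rates of 30% and 10% and an assumed capture of one half.

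The documents do not show that harms in general will be under-counted. The caveat in section 1.3.12 about rare outcomes does not answer the point, because section 1.3.4 places dizziness and ataxia among the commonest side effects. This is a cheap improvement to a secondary objective. It does not touch the primary analysis.

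**What to change.** In Appendix D (before item 5), Appendix F (before item 5) and Appendix G (before item 9), add one item for dizziness and one for unsteadiness, on the 1-5 none-to-severe scale already used for nausea. Keep the open question after them.

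Name these items in sections 1.1.2 and 1.3.10 as the dizziness/unsteadiness comparison under Objective 4, and state how they will be scored, for example any against none by the chi-square test already planned. Use the Appendix D item as the reading before IV sedation. It is free of IV midazolam and fentanyl but not of the oral pre-procedure drugs. It may also precede the peak concentration, which section 1.3.4 puts at 2-4 hours, since dosing may be as little as one hour before the procedure. The later readings are therefore needed too.

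The cost is two short items on three existing forms, with no new visit and no change in care. Reported rates will rise in both arms, partly from co-medication, and the report should say that they were prompted.

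Optional and minor: yes/no fields in the Appendix C record review for seizure-like activity, aspiration of emesis and hospital transfer. These would tidy the record but would not give a powered comparison.
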